4.5 Treatment allocation

The IMP is supplied as opaque, size 0 capsules, in a high-density polyethylene bottle containing 60 capsules. One bottle will contain sufficient capsules for one treatment period. Each capsule contains 30 mg LAT8881 plus [REDACTED] excipients. Placebo capsules contain the excipients [REDACTED] only (without LAT8881).

On Day 1, after the first baseline period, eligible subjects will be enrolled and randomised to LAT8881 or placebo. They will receive the investigational medicinal product (IMP) twice daily for four weeks (Days 1 to 28). On the morning of Day 28 they will return to the clinic for their end of first treatment visit and will take an IMP capsule in the morning during their clinic visit. They will take their final IMP dose for this treatment period in the evening.

The first treatment period will be followed by a washout period of two weeks (Days 29 to 42 inclusive) and then a second baseline period of one week (Days 43 to 49 inclusive). Over these days (i.e. Days 29-49 inclusive) subjects will not take any IMP.

On Day 50, subjects will return to the clinic and cross over to receive the second treatment (either LAT8881 or placebo, whichever treatment was not received in the first treatment period) twice daily for four weeks (Days 50 to 77). On the morning of Day 77, they will return to the clinic for their end of

second treatment visit and will take an IMP capsule in the morning during their clinic visit. They will take their final IMP dose for this treatment period in the evening.

5 Assessment Schedule

5.1 Screening, First Baseline Period, First Treatment Period and Washout

Visit No	Screening Stage 1	Screening Stage 2 (First Baseline)	First Treatment Period			Washout
	1	2	3	4		
Study Day	-28 to -8	-7 to -1	1	14 ± 1	28 ± 1	29 (+/-1) to 42 (+/-1)
Written informed consent	X					
Eligibility assessment	X					
Pain diary training	X					
Confirmation of eligibility			X			
Enrolment			X			
Randomisation			X			
Medical history, demographics	X					
Height, ¹ weight	X		X	X	X	
PD-Q	X		X			
12 lead ECG	X		X ²		X ²	
Vital signs	X		X ³	X	X	
Physical examination ⁴	X		X ⁵	X ⁵	X ⁵	
Concomitant medications	X		X	X	X	
Clinical laboratory safety testing ⁶	X		X ⁷		X ⁸	
Pregnancy test ⁹	X ⁹		X ¹⁰			
██████████			█		█	
IMP administration			X ¹³	X	X ¹³	
Adverse event assessment	X ¹⁴	X ¹⁴	X	X	X	
Blood sampling for PK analysis ¹⁵			X ¹⁶		X ¹⁶	
Daily NPRS ratings ¹⁷		X	X ¹⁸	X	X ¹⁸	X
Short form BPI assessment			X		X	
Short form McGill questionnaire 2			X		X	
Neuropathic Pain Symptom Inventory			X		X	
Beck Depression Index-II			X		X	
PGIC					X	

- 1 Height measured only at screening
 2 Pre-dose
 3 Pre-dose and 0.5 hours post-dose
 4 Includes assessment of area of pain
 5 Targeted physical examination
 6 Haematology, biochemistry, urinalysis
 7 Results of clinical laboratory tests not required prior to dosing
 8 Females of child bearing potential only
 9 Blood pregnancy test
 10 Urine pregnancy test
 █
 █
 13 Supervised administration
 14 SAEs only (UK subjects only)
 15 PK subjects only
 16 Pre-dose and up to 6 hours post-dose
 17 Each evening, throughout baseline, treatment and washout periods
 18 Additional ratings pre-dose and up to 6 hours post-dose in PK subjects

5.2 Second Baseline Period, Second Treatment Period and Follow Up

Visit No	Second Baseline Period	Second Treatment Period			End of Study
		5	6	7	
Study Day	43 to 49	50 ± 1	63 ± 1	77 ± 1	91 ± 2
Weight		X	X	X	X
12 lead ECG		X ¹⁹		X ¹⁹	
Vital signs		X ²⁰	X	X	X
Physical examination ²¹		X ²²	X ²²	X ²²	X ²²
Concomitant medications		X	X	X	X
Clinical laboratory safety testing ²³		X ^{19,24}		X ¹⁹	X
IMP administration		X ²⁷	X	X ²⁷	
Adverse event assessment		X	X	X	X
Blood sampling for PK analysis ²⁸		X ²⁹		X ²⁹	
Daily NPRS ratings ³⁰	X	X ³¹	X	X ³¹	
Short form BPI assessment		X		X	
Short form McGill questionnaire 2		X		X	
Neuropathic Pain Symptom Inventory		X		X	
Beck Depression Index-II		X		X	
PGIC				X	

19 Pre-dose

20 Pre-dose and 0.5 hours post-dose

21 Includes assessment of area of pain

22 Targeted physical examination

23 Haematology, biochemistry, urinalysis

24 Results of clinical laboratory tests not required prior to dosing

27 Supervised administration

28 PK subjects only

29 Pre-dose and up to 8 hours post-dose

30 Each evening throughout baseline and treatment periods

31 Additional ratings pre-dose and up to 8 hours post-dose in PK subjects

6 Interim Analysis

There is no interim analysis planned for this study.

6.1 Unblinding and Dissemination of Results

There is no interim analysis planned for this study, so this section is not applicable.

7 Efficacy and Safety Endpoints

7.1 Primary Efficacy Endpoints

1. *Absolute change in mean pain score, using an 11 point NPRS, from baseline to the last week of each treatment period. Pain is recorded once daily in a subject diary in the evening, and should reflect the subject's average pain over the last 24 hours*

Baseline mean pain for each subject is defined as the mean of the last five available ratings of daily pain, recorded in each baseline period.

End of treatment mean pain for each subject is defined as the mean of the last five available ratings of daily pain, recorded in the last 7 days of each 4 week treatment period.

7.2 Secondary Efficacy Endpoints

1. *Change in NPRS score at 0.5, 1, 2, 4 and 6 hours after the first dose of IMP in each treatment period, compared with the score recorded no more than 60 minutes before the first dose of IMP in that treatment period (PK subjects only)*
2. *Change in NPRS score at 0.5, 1, 2, 4 and 6 hours after a single dose of IMP, following four weeks treatment with IMP in each treatment period, compared with the score recorded no more than 60 minutes before this dose (PK subjects only)*
3. *Change in mean pain scores from baseline after 1, 2 and 3 weeks of dosing with IMP in each treatment period, using an 11 point NPRS. Pain scores at weeks 1, 2 and 3 are defined as the mean of the last five available ratings of daily pain in the subject diary, recorded in the previous 7 days of treatment*
4. *30% responder rate, based on the proportion of subjects achieving $\geq 30\%$ reduction in mean NPRS from baseline to the end of 4 weeks treatment in each treatment period*
5. *50% responder rate, based on the proportion of subjects achieving $\geq 50\%$ reduction in mean NPRS from baseline to the end of 4 weeks treatment in each treatment period*
6. *Maximum change in mean NPRS from baseline after 1, 2, 3 or 4 weeks treatment in each treatment period*
7. *Change in functioning from baseline to the end of 4 weeks treatment in each treatment period, as measured by the BPI interference scale*
8. *Change in pain characteristics and intensity from baseline to the end of 4 weeks treatment in each treatment period, as assessed by the SF-MPQ-2*
9. *Change in neuropathic pain symptoms from baseline to the end of 4 weeks treatment in each treatment period, as assessed by NPSI*

10. *Change in emotional functioning from baseline to the end of 4 weeks treatment in each treatment period, as assessed by the BDI-II*
11. *PGIC at the end of each four week treatment period*
12. *Paracetamol (rescue medication) use per week over each treatment period compared with the preceding baseline*

7.3 Safety Endpoints

1. *Physical examinations and vital signs*
2. *ECG*
3. *Clinical chemistry and haematology analyses*
4. *Urinalysis*
5. *Number and type of Treatment Emergent Adverse Events (TEAEs), including serious adverse events (SAEs), and suspected unexpected serious adverse reactions (SUSARs)*
6. *Concomitant medications*

7.4 Pharmacokinetic endpoints

1. *Pharmacokinetic parameters: C_{max} , T_{max} , AUC_{0-inf} in each treatment period, after a single dose and at the end of four weeks treatment in PK subjects*

7.5 Exploratory endpoints

1. *Association between change in mean NPRS from baseline to the end of four weeks treatment and selected subject baseline characteristics, including clinical diagnosis and pre-treatment [REDACTED]*
2. *Change from baseline in [REDACTED] [REDACTED] to the end of 4 weeks treatment, in each treatment period*
3. *Correlation between plasma LAT8881 concentration and the change in mean NPRS from baseline to the end of four weeks treatment in PK subjects*
4. *Change in mean NPRS score from baseline to the last week of each treatment period, after omission of subjects with the 25% most variable first baseline NPRS scores*

8 Statistical Methods

Efficacy endpoints will be summarized in a descriptive manner and analyzed using statistical methods described in section 11.7. The level of significance for statistical tests will be 0.05 and all tests will be two-sided. All p-values will be displayed to four decimal places, with p-values less than 0.0001 presented as '<0.0001' and p-values greater than 0.9999 presented as '>0.9999'. All analyses will be done using SAS [REDACTED]

Safety endpoints will be summarised in a descriptive manner.

Continuous data will be reported using the following descriptive statistics:

1. Number of observations (n)

2. Mean and standard deviation (SD)
3. Minimum (min) and maximum (max)
4. Median

Minimum and maximum values will be reported to the precision of the endpoint reported with maximum of three decimal places; the mean will be presented with one decimal place more and the standard deviation two decimal places more than the precision of the endpoint reported. Categorical data will be presented using frequency (n = number of subjects; m = number of events) and percentage (%).

Listings will be provided for all data recorded in eCRF to study subject profiles. All listings will be sorted by treatment sequence, subject ID, study period and date (if applicable). Unscheduled visit data will only be listed and not included in summaries.

8.1 Handling Missing/Incomplete Data

For medications / adverse events, if start date is partial then the first day/first month will be imputed. If end date is partial then the last day/last month will be imputed. Medications/Adverse Events with missing year will be considered as concomitant/TEAE respectively (assuming worst case). If an AE started during the same month/year as first dose of IMP in period 1, then the date will be imputed as first IMP date and considered as TEAE (assuming worst case).

Flags identifying the study period for the start/stop dates for prior/ concomitant medications and adverse events will be generated (see Sections 10.6, 10.9). Imputed dates will be used for analyses and collected dates recorded in database will be listed.

The method for missing data imputation for the primary endpoint will be discussed during the blinded review meeting prior to database lock.

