10.6 Prior and Concomitant Medications

Medications that ended before first dose of IMP (LAT8881 or placebo) in the first treatment period are considered as prior medications. If medications are ongoing or they start on or after first dose of IMP (LAT8881 or placebo) they are considered concomitant.

Medications that started on or after first dose of IMP in treatment period 1 or during wash-out will be counted in the first treatment period and allocated to the treatment received in treatment period 1.

Medications that started on or after first dose of IMP in treatment period 2 will be counted in the second treatment period and assigned to the treatment received in treatment period 2. If medication occurred in first study period and continued to second, it will be counted in both study periods (as 'New' in period 1 and 'Ongoing' in period 2).

Programming note for concomitant medications:

- Period 1, Ongoing - if CM start date is prior to first dose of IMP in period 1 and end date is on or after first dose of IMP in period 1.
- Period 1, New - if CM start date is on or after first dose of IMP and before first IMP date in period 2.
- Period 2, Ongoing - medications that were new or ongoing in period 1, with end date on or after first IMP date in period 2.
- Period 2, New - if CM start date is on or after first dose of IMP in period 2.

Concomitant medications will either be flagged as "Ongoing" or "New" within a study period, but not in both.

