10.7 Rescue Medications

Rescue medications will be flagged for analysis. Additionally, cumulative dose in milligrams (mg) will be calculated within each study period. If a subject has ongoing rescue medication in both study periods, then the cumulative dose within each study period will be calculated.

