10.9 Adverse Event Flags

Treatment emergent adverse event (TEAE) flags will be marked for adverse events if they occurred or worsened on or after the first administration of IMP in the first study period. Adverse events occurring during screening and first baseline period will not be considered as TEAEs.

If the events cannot be determined as TEAE due to partial dates, then the worst case will be considered and they will be flagged as TEAE in the respective study period based on AE start date.

Related Adverse Events will be flagged for Possibly, Probably and Definitely Related adverse events. Adverse events that started on or after first dose of IMP in treatment period 1 or during wash-out will be counted in the first treatment period and allocated to the treatment received in treatment period 1. AEs that commenced on or after first dose of IMP in treatment period 2 will be counted in the second treatment period and assigned to the treatment received in treatment period 2. If an adverse event occurred in first period and continued to second period, it will be counted in both study periods (as 'New' in period 1 and 'Ongoing' in period 2). If AEs have same month/year as IMP date, then the

decision regarding whether to consider them as 'Ongoing' or 'New' within the period will be decided in the blinded review meeting.

Suspected unexpected serious adverse events (SUSARs) will be flagged by the Sponsor and included in analyses datasets.

Programming note for adverse events:

- Period 1, Ongoing - if AE start date is prior to first dose of IMP in period 1 and end date is on or after first dose of IMP in period 1.
- Period 1, New - if AE start date is on or after first dose of IMP and before first IMP date in period 2.
- Period 2, Ongoing - AEs that were new or ongoing in period 1, with end date on or after first IMP date in period 2.
- Period 2, New - if AE start date is on or after first dose of IMP in period 2.

Adverse events will either be flagged in "Ongoing" or "New" within a study period, but not in both.

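### Partial stop dates are imputed to month-end or year-end with no cap, so medications and some AEs that ended off drug can be counted under the Period 2 treatment as well

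*SAP*

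**What the plan says.** SAP 8.1 imputes outward at both ends: "For medications / adverse events, if start date is partial then the first day/first month will be imputed", and for stops "If end date is partial then the last day/last month will be imputed". It then states: "Imputed dates will be used for analyses and collected dates recorded in database will be listed". Records with no year have their own rule: they are classed as concomitant or treatment-emergent, and no stop date is built. One boundary is anchored. An AE starting in the same month as the first Period 1 dose is given that dose date. Stop dates, medications and the Period 2 boundary have no such anchor.

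These dates then drive allocation to periods:

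- **Medications (SAP 10.6).** The Period 2 Ongoing flag applies to "medications that were new or ongoing in period 1, with end date on or after first IMP date in period 2".
- **AEs (SAP 10.9).** The matching rule is "AEs that were new or ongoing in period 1, with end date on or after first IMP date in period 2". The same section sends AEs sharing month and year with an IMP date to blinded review, to choose between the Ongoing and New labels.
- **Rescue medication (SAP 10.7).** "If a subject has ongoing rescue medication in both study periods, then the cumulative dose within each study period will be calculated". No formula linking dates to mg is given.

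The by-treatment concomitant medication table (SAP 11.5) and SOC/PT AE table (SAP 11.7.1.2) count Ongoing as well as New records. The overall AE table (SAP 11.7.1.1) counts New only.

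**The concern.** Between the last Period 1 dose (Day 28) and the first Period 2 dose (Day 50) no IMP is taken. A record that closed in that gap belongs to Period 1 under the SAP's own allocation rule. If its stop day is missing, month-end imputation can move the stop to Day 50 or later. The record then also appears under the second treatment, even when site staff had already recorded it as finished at Visit 5. That date is impossible, not merely conservative.

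Paracetamol use is a named secondary endpoint (SAP 7.2, item 12), and cumulative mg is the only dose summary that SAP 11.5.1 fixes in advance. If mg is built from start and stop dates, moving both outward gives the longest course the recorded months allow.

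**Working it through.** The documents give no figure for date imputation, so there is none to reproduce.

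**Inputs.** Day 1 to Day 28 is the first treatment window, Days 29-42 washout, Days 43-49 second baseline, and Day 50 the first Period 2 dose (SAP 4.5, 10.4). Assumption: Day 1 is equally likely on each of the 365 dates of 2019. Visit windows are ignored.

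**1. Carry-over, stop month known.** A stop on Day d moves to the end of its month. It reaches Day 50 only if Day 50 lies in the same calendar month. Let g = 50 − d. For g up to 28, each of the 12 month-ends in the year rules out g start dates, so

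share carried = (365 − 12g) / 365.

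| True stop | g | Share carried |
|---|---|---|
| Day 29 | 21 | (365 − 252)/365 = 31% |
| Day 42 | 8 | (365 − 96)/365 = 74% |
| Days 29-42 | mean 14.5 | (365 − 174)/365 = 52% |
| Days 43-49 | mean 4 | (365 − 48)/365 = 87% |
| Days 29-49 | mean 11 | (365 − 132)/365 = 64% |

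Full enumeration agrees: 2,674 of 5,110 for Days 29-42, 2,219 of 2,555 for Days 43-49 and 4,893 of 7,665 for both together. For Days 1-28 it gives 480 of 10,220, or 5%. Carried stops from Days 29-42 extend 1 to 23 days into Period 2, mean 9.0. If only the year is known, 96% of stops on Days 29-42 are carried.

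*Carried:* Day 1 = 9 September 2019, washout 7-20 October, Day 50 = 28 October. The imputed stop, 31 October, is Day 53. *Not carried:* Day 1 = 20 September 2019, washout 18-31 October. The imputed stop, 31 October, is Day 42.

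**2. Course length.**

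- Both days missing, same month: the whole month, 28-31 days. If the course straddles a month-end, it becomes two months.
- Start known, stop day missing: a 1-day course averages 15.7 days and 11% reach 28 days. For a 3-day course 18% do, and for a 7-day course 31%.
- Start known, stop month missing: a 1-day course runs to 31 December, mean 183 days.

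**3. Where the extra days fall.** A 3-day course lying wholly within Days 29-49, with both days missing, averages 32.5 imputed days: 7.7 on Days 1-28, 17.1 on Days 29-49 and 7.7 on Days 50-77. In 67% of cases it reaches Day 50. For courses wholly within Days 29-42, the two treatment windows receive 10.0 and 5.2 days, and 56% reach Day 50. The true contribution to either window is zero. If mg is days times a constant daily dose (an assumption), 7.7 days is 7.7 g at 1 g/day, 15.4 g at 2 g/day and 30.8 g at 4 g/day in each window.

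**4. Scaling.** Let p be the share of records ending on Days 29-49 whose stop day is missing. About 0.64 × p of those records are carried: 3.2% if p is 5%, 12.8% if p is 20%. The documents give no value for p; these two are illustrative.

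**The case against.** The other side has several fair points.

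- **Blinded review.** With the month known, carry-over happens only when the stop shares its month with the first Period 2 dose. The SAP 10.9 clause is not expressly limited to start dates, so it may reach these AEs. This stands in part. The clause offers only a choice of label within the period, and it does not cover medications.
- **New-only table.** The overall AE table is unaffected. This stands in full.
- **Dose formula.** SAP 10.7 does not say that mg is computed from dates. This stands, so the effect on mg is conditional.
- **Few partial dates.** Protocol 10.3 and 10.4 review AEs and medications at each visit, and 14.2.3 queries missing data. Partial stops may be rare. This stands as a limit on size.
- **Deliberate conservatism.** SAP 8.1 calls its missing-year and AE-start rules worst case. That does not justify a stop date later than the visit at which the record was already closed.

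A reader might infer three stronger points that the documents do not support. First, that any partially dated course becomes a month or more: this needs both days or the stop month missing. Second, that 64% describes washout: it pools washout (52%) with second baseline (87%). Third, that the dose from the whole imputed course (32.5 days, 65 g at 2 g/day) can be set against a 28-day ceiling of 112 g (4 g × 28): most of those days lie outside either treatment window.

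**Conclusion.** The concern holds in limited form. The rule has no cap, the imputed dates are analysed, and the period flags depend on them, so a record that ended off drug can be counted under both treatments. Medications are clearly exposed; AEs are exposed where blinded review does not settle them. The chance per day-missing stop is about 52% on Days 29-42, 87% on Days 43-49 and 5% on Days 1-28, assuming evenly spread start dates and a known month.

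A reader might infer bias towards one arm. The documents do not support that: the rule ignores treatment and applies to both randomised sequences, so records are carried in both directions. The result is blurring. It touches descriptive rescue and safety summaries, not the primary NPRS analysis, and its overall size depends on a share of partial dates that the documents do not give.

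**What to change.** In SAP 8.1, impute a partial stop date as the earliest of month-end (or year-end), the date of the visit by which the record was reported as stopped, and last contact. A record closed at or before Visit 5 then cannot receive a stop date on or after the first Period 2 dose.

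For cumulative paracetamol dose, bound both imputed dates by the visits between which the use was reported, and show the total with and without partially dated records. SAP 10.7 should also state how mg is calculated.

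The cost is a few sentences and some derivation code before unblinding. The cap needs the visit at which each record was closed. The protocol's visit-by-visit review should supply it, but the documents do not show how the eCRF stores it, so this should be confirmed. A few courses that truly ran longer may be slightly shortened.

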8.2 Handling Outliers

Laboratory results with modifiers will be analyzed with the maximum or minimum value defined without the modifiers. For example, a value of "<5" will be considered as "5" for summaries.

8.3 Multiplicity Adjustment

Since there is only one primary endpoint defined in the study as per the protocol, multiplicity adjustment is not required. Although, hypothesis tests for secondary and efficacy endpoints will be performed and caution must be taken when interpreting these results. Adjusted p-values using Bonferroni method may be derived for post-hoc analyses if deemed necessary.

9 Analysis Populations

Membership of the analysis populations will be reviewed and finalized during the blind review of the data conducted prior to database lock.

9.1 Full Analysis Set

The Full Analysis Set (FAS) consists of all subjects enrolled and randomised into the study. The FAS population will be used for summaries of subject disposition, demographic and baseline characteristics.

Subjects will be analysed according to the treatment group they were assigned at randomisation.

